2.2.2. Secondary Objectives

The secondary objectives of this study are the following:

- To assess behavioral/neuropsychiatric changes correlated with domains of attention, sleep, and a target behavior chosen by the parent/caregiver, using objective tests of CNS function for GNX compared with PBO as adjunctive therapy at the end of the 17-week double-blind phase.
- To assess the safety and tolerability of GNX compared with PBO as adjunctive therapy at the end of the 17-week double-blind phase.
- To assess PK parameters in subjects receiving GNX doses up to 63 mg/kg/day (1800 mg/day maximum) throughout the study.

- To assess the long-term efficacy of GNX when administered as adjunctive therapy throughout the open-label phase.
- To assess the long-term safety and tolerability of GNX when administered as adjunctive therapy throughout the open-label phase.

[REDACTED]

[REDACTED]

- [REDACTED]
- [REDACTED]
- [REDACTED]
- [REDACTED]

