3.4. Discussion of Study Design, Including the Choice of Control Group

Dosing will be based on doses that have been shown to be safe in children and adults in multiple studies with normal volunteers and individuals with epilepsy. In this current study, subjects will be randomized (1:1 ratio) to receive either GNX or PBO, prescribed in increments of 15 mg/kg/day up to 63 mg/kg/day (maximum 1800 mg/day), as an oral suspension for up to 17-weeks. The double-blind phase will be followed by an open-label phase in which all subjects will receive GNX up to an additional 3 years or more, providing long-term safety and tolerability data on GNX. Administration of GNX adjunctive therapy to background AEDs provides standard-of-care therapy in addition to any benefit that investigational product might provide.

Subjects will be randomized to receive either GNX or PBO, prescribed in increments of 15 mg/kg/day up to 63 mg/kg/day (maximum 1800 mg/day) as an oral suspension.

- 6 mg/kg three times daily (TID) (18 mg/kg/day) suspension -Days 1-7
- 11 mg/kg TID (33 mg/kg/day) suspension -Days 8-14
- 16 mg/kg TID (48 mg/kg/day) suspension - Days 15-21
- 21 mg/kg TID (63 mg/kg/day) suspension - Days 22-28

Any subject not tolerating the next dose step can be maintained at the lower dose step for additional days before advancing to next dose. If the next dose is still not tolerated, they can drop back to the next lower dose step. A minimum dose of 33 mg/kg/day and 900 mg/day must be maintained. Dose changes including alternative dosing paradigm (e.g., lower dose during the daytime and higher dose in the evening) should be discussed with the sponsor medical monitor prior to making the change or within 48 hours of making the change. The higher dose in the evening is expected to be better tolerated due to the proximity to bedtime. However, tolerability management and the final decision to adjust drug dosages lies with the Principal Investigator. Any subject who is unable to be maintained at the minimum dose should contact the sponsor to discuss continued investigational product dosing. Subjects who discontinue investigational

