#### 1.2.5 Open-Label Phase Endpoints

Except for the changes in seizure frequency during the titration phase and during the maintenance phase, the same efficacy, exploratory, quality of life, and safety endpoints for the DB phase will also be used for the open-label phase. In addition, the Tanner Staging, which is performed only at Screening in the DB phase of the study unless the subject does not enter the OLE phase, is another safety endpoint. When the DB phase is completed in all the subjects, a cutoff date will be declared for purposes of NDA submission and all open label data collected up to the cutoff will be analyzed. When the full study is completed, the open-label data will be re-analyzed.

The results for the open-label phase should be interpreted cautiously because there is no control group in that phase, and the intent-to-treat principle may be compromised since several subjects may not enter the phase and, among those entering, several may withdraw from the study prior to its completion. In addition, there is no blinding during the open-label phase.

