### 1.3 Summary of the Study Design

#### 1.3.1 General Study Design and Plan

This is a phase 3 global, DB, randomized, PBO-controlled trial of adjunctive GNX treatment in children and young adults with CDD. The trial consists of a 6-week prospective baseline period to collect seizure data, followed by a 17-week DB treatment phase, which is then followed by a long-term open-label phase.

[figure not shown]
The double blind phase includes 6 weeks prospective baseline, 4 weeks of titration followed by 13 weeks of dose maintenance. After meeting the eligibility criteria, children and young adults

aged 2-21 years (inclusive) with CDD will be randomly assigned to receive GNX or PBO (1:1 ratio) for 17 weeks in addition to their standard anti-seizure treatment. Recruitment will stop after approximately 100 children and young adults have been enrolled. Participants will be titrated to 63 mg/kg/day (max 1800 mg/day) over 4 weeks, and then maintained at that dose for another 13 weeks. Subjects who are not able to tolerate 63 mg/kg/day (or 1800 mg/day maximum) may be maintained on a lower dose after discussion with the Sponsor. A minimum dose of 33 mg/kg/day or 900 mg/day is required during the DB phase.

After completing the initial 17-week, DB, PBO-controlled phase, all subjects will be treated with GNX in the open-label phase of the study. GNX subjects will continue GNX treatment and PBO subjects will titrate onto GNX. To maintain the blind, subjects initially randomized to GNX will undergo a false titration (increasing PBO doses) for 4 weeks, while PBO subjects will titrate up to 63 mg/kg/day GNX (1800 mg/day maximum) during the same time phase (Figure 1). The open-label phase is estimated to take an additional 3 years. It will continue until the sponsor terminates the program or GNX has been approved and marketed the investigational product in the subjects' respective country.

Participants who complete the study or discontinue investigational product treatment before the end of the study will undergo a 2-week taper phase after which he/she will return to the site 2 weeks postdose for a safety follow up visit. Subjects who discontinue investigational product treatment before the completion of the DB phase will continue to be followed per protocol and at minimum maintain daily seizure diary entry until the DB phase is completed. These subjects will also return to the site 2 weeks after the taper for safety follow-up assessments.

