## 2.2 Definitions of Analysis Populations (Analysis Sets)

### 2.2.1 Safety and Intention-to-Treat (ITT) Population

This population comprises all randomized subjects who received at least one dose of study drug. In addition to being the population for the safety analyses, it is the primary population for the efficacy and neurosteroid level analyses.

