## 9.1 Adverse Events

Adverse events (AEs) will be coded by System Organ Class (SOC) and Preferred Term (PT) using the MedDRA®, version 16.0 or higher. The verbatim term will be included in the AE listings. Except where indicated, the summary tables will include only TEAEs. All AEs, treatment-emergent or otherwise, will be presented in subject data listings.

A treatment-emergent adverse event (TEAE) is defined as an AE that starts or worsens on or after the first dosing day of study drug. The AE analyses for the main 17-week DB treatment phase of the study will include AEs that start or worsen during that phase and will not include AEs that start or worsen during the OLE phase; ie, they will not include any AEs starting or worsening on or after the first dosing day of the OLE phase.

For the OLE phase of the study, the AEs will be summarized over just the OLE phase as well as over the entire study (combined DB and OLE phases) but the classification by the DB treatment applies only for the OLE phase summary. The summarization over the entire study will include AEs in the DB phase only from subjects who were in the GNX group during the DB phase, regardless of whether they entered the OLE, and all the subjects from the OLE phase; i.e., it will include only the AEs following GNX exposure. The summarizations over just the OLE phase will include TEAEs that start or worsen after the first day of the OLE phase; the summarizations over the entire study will include TEAEs that start or worsen on or after the first dosing day of GNX.

The TEAEs will be summarized as the number of events and the number and percentage of subjects with TEAEs. Subjects who report the same PT on multiple occasions will be counted once for the PT: under the highest severity (severe > moderate > mild) when summarized by severity and under the closest relationship (related > unrelated) to study drug when summarized by relationship. TEAEs with missing relationships will be considered as related.

If a subject reports multiple PTs for a SOC, the subject will be counted only once for that SOC. For the counting of events, all the PTs will be included in the counts, even when subjects have multiple PTs.

Pre-treatment emergent AEs by will be summarized by SOC and PT (only for the DB period summary).

TEAEs will be summarized as below.

- An overview table of TEAEs, including number of events and number (%) of subjects with
  - TEAEs

- serious TEAEs (Treatment-emergent SAEs)

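### No exposure-adjusted or onset-interval AE summary is planned for the open-label and entire-study tables, so their crude percentages cannot be read as long-term incidence

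*SAP*

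**What the plan says.** Long-term safety is a stated secondary objective (Protocol 2.2.2): "To assess the long-term safety and tolerability of GNX when administered as adjunctive therapy throughout the open-label phase".

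The AE statistic is fixed in SAP 9.1: "The TEAEs will be summarized as the number of events and the number and percentage of subjects with TEAEs". The periods follow in the same section: "For the OLE phase of the study, the AEs will be summarized over just the OLE phase as well as over the entire study". The listed tables (overview, SOC and PT, severity, relationship, SAEs, discontinuations, dose reductions, events of special interest) use this format throughout. On who contributes to the entire-study table, SAP 9.1 says: "The summarization over the entire study will include AEs in the DB phase only from subjects who were in the GNX group". That table is not split by double-blind arm. Protocol 9.8 leaves the detail to the SAP.

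Follow-up in these tables varies for several reasons:
- SAP 2.2.1 on the safety population: "This population comprises all randomized subjects who received at least one dose of study drug".
- SAP 1.3.1: "The open-label phase is estimated to take an additional 3 years". Protocol 3.4 says that "all subjects will receive GNX up to an additional 3 years or more".
- SAP 1.2.5: once all subjects have completed the double-blind phase, "a cutoff date will be declared for purposes of NDA submission". The open-label data are analysed then and again at study end.
- SAP 1.2.5 also expects some subjects to withdraw during the extension.

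SAP section 9 does summarise days on study drug over the OLE alone and over the entire study. It tabulates repeated safety assessments by scheduled time point.

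**The concern.** A crude percentage is the share of subjects with at least one event during whatever time each was observed. It rises with observation time even when the underlying rate is constant. In a fixed 17-week phase this does little harm. In an open-ended phase with staggered entry, a data cut and withdrawals, the figure mixes risk with length of follow-up.

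Two comparisons that readers will make are therefore unsafe: double-blind against open-label, and NDA cutoff against study end. A constant rate would look like growing risk. Timing is lost as well: within the OLE, events confined to the first months and events that keep accruing can give the same percentage. For a drug meant for long-term use, that distinction is central to the long-term tolerability objective.

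The SAP standardises for observation time elsewhere. Seizure counts are divided by days with diary data (7.1.2), and open-label seizure endpoints are reported over stated numbers of weeks (7.2).

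**Working it through.** The plan gives no AE rate, open-label dropout rate or accrual period, so there is no planned figure to reproduce. The check has a text part and an illustration on assumed inputs.

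**Text.** SAP 1.2.5, 2.1 and section 9, and Protocol 9.8, contain no person-time denominator for AEs, no analysis of time to first event and no table by onset interval. The double-blind/OLE split is the only division by time.

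**Range of GNX time.** Minimum: one dose. Maximum: 17 weeks plus about 3 years = 17 × 7 / 365.25 + 3 = 0.326 + 3 = 3.33 years.

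**Illustration: one assumed true rate, h = 0.20 per year, constant.**

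Everyone followed for time t: crude % = 1 − exp(−h t)
- t = 0.326 (17 weeks): 1 − exp(−0.0652) = 6.3%
- t = 1: 1 − exp(−0.2) = 18.1%
- t = 3: 1 − exp(−0.6) = 45.1%

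OLE at the data cutoff, follow-up assumed uniform on 0 to R years: crude % = 1 − (1 − exp(−hR)) / (hR)
- R = 1: 1 − 0.1813 / 0.2 = 9.4%
- R = 2: 1 − 0.3297 / 0.4 = 17.6%

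OLE at study end, maximum 3 years, assumed exponential dropout d per year: crude % = h / (h + d) × (1 − exp(−3(h + d)))
- d = 0.1: 0.667 × (1 − exp(−0.9)) = 39.6%
- d = 0.4: 0.333 × (1 − exp(−1.8)) = 27.8%

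So one rate shows as 9.4% to 17.6% at the cutoff and 27.8% to 39.6% at study end. The rate per person-year is 0.20 in every case. At h = 0.05 the spread over the same patterns (cutoff with R = 1 up to complete 3-year follow-up) is 2.5% to 13.9%.

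**Timing.** Take d = 0.2 and a 3-year maximum. A constant 0.20 per year gives 0.5 × (1 − exp(−1.2)) = 34.9%. A hazard of 1.37 per year in the first 17 weeks and zero afterwards gives 1.37 / 1.57 × (1 − exp(−1.57 × 0.326)) = 34.9%. The crude table cannot tell these apart.

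**What can be recovered from the planned tables.** Event counts divided by total drug time (n × mean days / 365.25) give an approximate event rate. With invented numbers, 200 events, n = 100 and mean 600 days: 100 × 600 / 365.25 = 164.3 person-years, and 200 / 164.3 = 1.22 events per person-year. Subjects with a first event per person-year at risk cannot be obtained this way, because time after the first event must be removed subject by subject. Risk by period cannot be obtained either.

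**The case against.** The strongest reply is that this is a reporting refinement. The open-label results are descriptive, no test compares AE percentages across phases or cuts, and SAP 1.2.5 tells readers to be cautious. All AEs are listed by subject, so rates can be added at any time. Event counts and the exposure summary already allow a rough rate. Most of this stands, and it limits the point to interpretation of a secondary objective. It does not remove it. The caution in SAP 1.2.5 rests on the lack of a control group, withdrawals and lack of blinding, and does not mention unequal observation time. The hand-derived rate is not pre-specified and can be driven by repeat events in a few subjects. It may also mismatch numerator and denominator, because exposure counts days on drug while the TEAE definition sets no end to the risk window after the last dose.

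Some stronger readings are tempting and not supported:
- A reader might infer that long-term safety cannot be assessed at all from the planned tables. Laboratory tests, vital signs and ECG are tabulated by visit, Tanner stage by open-label visit, and AEs separately for the double-blind and open-label phases.
- A reader might infer that the tables set subjects with 17 extra weeks on GNX against those without. The entire-study table pools them in one column, and the open-label table counts both arms from the start of that phase.
- A reader might infer that most subjects will be recent entrants at the cutoff. The documents give no accrual rate.

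**Conclusion.** The point holds as a limit on interpretation. The crude open-label and entire-study percentages pool follow-up from as little as one dose to about 3.33 years. They should not be read as long-term incidence or compared across phases or data cuts. The size depends on assumptions that the documents do not supply. At an assumed constant 0.2 per year the percentage runs from 6% at 17 weeks to 45% with complete 3-year follow-up. The 45% is an upper figure for that rate and horizon; with the assumed dropout it is about 28% to 40%. The direction does not depend on these inputs: for a given hazard pattern, the crude percentage cannot fall as follow-up lengthens. No primary result, error rate or data collection is affected.

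**What to change.** In SAP 9.1, keep the crude counts and percentages. For the OLE and entire-study tables of TEAEs, SAEs, AEs of special interest and AEs leading to discontinuation, add:

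1. Subjects with a first event per 100 person-years at risk.
2. Incidence by time since first GNX dose, for example 0 to 17 weeks and then 6-month intervals, with the number at risk in each. A single rate averages over time, so this table is needed to show whether risk changes. In the OLE-only version, subjects from the double-blind GNX arm enter at about week 17.

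State one at-risk window and use it for both numerator and denominator. It could run from first GNX dose (start of the OLE for the OLE-only table) to the earliest of first event, end of AE follow-up or data cutoff. Otherwise, restrict both events and time to on-drug days. The choice has to be written down because the present TEAE definition has no end.

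The cost is SAP wording and a few extra tables. The event and dosing dates are already collected.

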- treatment related TEAEs
- TEAEs by severity
- TEAEs leading to study drug discontinuation
- TEAEs leading to dose reduction or temporary study drug discontinuation
- TEAEs leading to death
- TEAEs by SOC and PT
- TEAE by SOC, PT, and Severity
- Study drug related TEAEs by SOC, PT
- Treatment-emergent SAEs by SOC and PT
- TEAEs leading to study drug discontinuation by SOC and PT
- TEAEs leading to dose reduction or temporary study drug discontinuation by SOC and PT
- TEAEs of special interest: rashes and the reproductive system and breast disorders system organ class
- TEAEs by PT

All AE tables will be sorted by SOC and PT in decreasing frequency of the number of subjects in the GNX group in the DB summaries and the combined groups in the OLE summaries; in case of tied frequencies, the sorting will be alphabetical.

For purposes of determining treatment emergent events, missing start and stop dates will be imputed as shown in the following table; however the actual dates, not the imputed ones, will display in the data listing.

Partial Missing Start or Stop Date	Imputed Start Date	Imputed Stop Date
Missing month, day, and year	First dose date	
Missing month and day, and the year is present	First dose date if the year is the same as the year of first dose date, else first dose date of the OLE if the year is the same as the year of the first OLE dose date, else January 1 of the AE start year.	December 31 of that year
Missing day, but year and month are present	First dose date if the year and month are the same as the year and month of first dose date, else first dose date of the OLE if the year and month are the same as the year and month of the first OLE dose date, else the 1 st of the AE start month.	Last day of that month
Missing month, but year and day are present	Assume day is also missing and impute as above	Missing month imputed as December

If an imputed start date is later than the stop date, then the stop date (after any needed imputations) will be used instead for the imputed start date.

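### The SAP's AE date-imputation rule can book placebo subjects' open-label ganaxolone events to double-blind placebo and drop them from the OLE and whole-study ganaxolone summaries

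*SAP*

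**What the plan says.** SAP 9.1 states the purpose of the table: "For purposes of determining treatment emergent events, missing start and stop dates will be imputed as shown in the following table". Two of its rows matter here.

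- The row "Missing month, day, and year" gives the first dose date and nothing else. The other rows name the first OLE dose separately, so this means the first double-blind dose.
- The row for a known year with month and day missing gives "First dose date if the year is the same as the year of first dose date, else first dose date of the OLE" if that year matches, and otherwise 1 January. The OLE is tried only when the AE year differs from the year of first dose. A date lacking only its month is treated the same way.

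One check follows the table: "If an imputed start date is later than the stop date, then the stop date" replaces it. This can only move a start earlier.

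The same section sets the table boundaries. For the double-blind summary, "they will not include any AEs starting or worsening on or after the first dosing day of the OLE phase". The whole-study summary "will include AEs in the DB phase only from subjects who were in the GNX group during the DB phase", together with all subjects' OLE data, and the SAP describes the result thus: "it will include only the AEs following GNX exposure". On dates, "the summarizations over the entire study will include TEAEs that start or worsen on or after the first dosing day of GNX". The OLE-only summary counts events starting later than the first OLE day. SAP 2.1 adds that double-blind outputs should hold only events that occurred before OLE entry.

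**The concern.** Subjects randomized to placebo receive GNX for the first time in the OLE (SAP 1.3.1). If one of them has an AE on open-label GNX and its start date is blank, or shows only the year of first dose, the rule places it on the first day of placebo. The event then counts under placebo in the double-blind table and is absent from the two summaries meant to show what happens on GNX. The table never consults the visit at which the AE was first reported, and a stop date deep in the OLE changes nothing. This contradicts the SAP's own description of both tables.

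Safety and tolerability are secondary objectives in both phases (Protocol 2.2.2). With about 50 subjects per arm, one misplaced subject moves a double-blind AE percentage by 1/50 = 2 points. The AEs of special interest (rash; reproductive system and breast disorders) are ones where single events may be noticed.

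**Working it through.** The documents give no figure on this point to reproduce, so the check applies the rule to example dates and then to an even spread of dates.

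**Inputs.** Week 17 is Study Day 17 × 7 + 1 = 120 (SAP 7.1.1 gives the same day), so the OLE starts about 119 days after first dose, with a ±3-day visit window. The OLE lasts about 3 years (SAP 1.3.1). Calendar dates below are illustrative.

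**Example.** Placebo subject, first double-blind dose 1 March 2019, first OLE (GNX) dose 28 June 2019, AE truly starting on GNX:

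| Recorded start | Stop date | Imputed start | Double-blind placebo | OLE-only | Whole-study GNX |
|---|---|---|---|---|---|
| blank | blank or 1 Oct 2019 | 1 Mar 2019 | yes | no | no |
| 2019 | blank or 1 Oct 2019 | 1 Mar 2019 | yes | no | no |
| 2020 | blank | 1 Jan 2020 | no | yes | yes |
| Sep 2019 | blank or 1 Oct 2019 | 1 Sep 2019 | no | yes | yes |

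The first two rows are wrong; the last two are right. For a subject randomized to GNX, the first two rows move the AE from the OLE into the double-blind GNX column, but it stays in the whole-study GNX summary.

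**How often both phases start in one year.** With first doses spread evenly over a year, (365 − 119)/365 = 246/365 = 67% (67% to 68% across the ±3-day window).

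**Share of placebo subjects' OLE AEs that is moved.**

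- Undated: 100%, since that row has no OLE branch.
- Year-only: a subject starting on day s of the year has 246 − s OLE days left in that year (none if s > 246). The average over all start days is 246²/(2 × 365) = 82.9 days. With even onset, 82.9/365 = 23% of AEs starting in the first OLE year, and 82.9/1095 = 8% over three years. A day-by-day run of the coded rule gave 22.7% and 7.6%.
- Month and year known: 0% move from the OLE to the double-blind phase. About 12% of double-blind onsets move the other way, to the first OLE day.

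**A boundary gap.** With first dose 1 October 2019 and OLE dose 28 January 2020, an AE dated only 2020 is imputed to 28 January 2020. The double-blind table excludes that day and the OLE-only table starts after it, so the AE is in neither phase table, only in the whole-study summary.

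**The case against.** The strongest objection is that few AEs should reach these rows. Protocol 8.1.1 requires start and stop dates, AEs are asked about at every visit and call, eCRF entry is expected within about 7 business days (Protocol 9.1), and omissions are queried (Protocol 9.2). A blank or year-only start would have to survive all that. The AE also stays visible: listings show the recorded date, with separate listings for deaths, SAEs, discontinuations and AEs of special interest (SAP 9.1.1). All of this stands. It limits the size of the problem but does not make the rule right.

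The rule is also cautious for its stated purpose, since a wholly undated AE defaults to treatment-emergent. That is true, but in a placebo-then-GNX design the same default also chooses the treatment.

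A reader might go further and infer that the rule raises the placebo rate and so narrows the double-blind difference. The documents do not support that. The rule is the same for both arms, and both take GNX in the OLE. If open-label AE rates are equal, it adds the same expected number of events to each column: the difference in event counts is unchanged, though a ratio would be diluted. Narrowing would need more such AEs in placebo subjects, for instance while titrating onto GNX, and nothing in the documents quantifies that.

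A reader might also conclude that about half of placebo subjects' year-only AEs are misplaced. Among subjects starting both phases in one year, the average open-label share of on-study time in that year is 1 − (119/246) × ln(365/119) = 46%. That applies only to AEs dated in the year of first dose. Year-only AEs from later years go to the first OLE dose or 1 January.

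**Conclusion.** The point holds as a defect in a stated rule. A blank start date, or a year-only date in the calendar year of first dose, is sent to the first double-blind dose even when other information puts the AE in the OLE. For placebo subjects, GNX events are then counted under placebo and lost from both the OLE and whole-study GNX summaries. For GNX subjects they change phase but remain in the whole-study summary.

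The shares (100% of undated; about 23% and 8% of year-only) rest on evenly spread first-dose dates and AE onsets. The first-year figure is the nearer guide for subjects with little OLE exposure at the submission cutoff in SAP 1.2.5. The number of affected AEs cannot be derived from the documents and is probably small. No net bias in the randomized safety comparison is shown. It is worth correcting because the correction is cheap and the present result contradicts the SAP's own aim.

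**What to change.** In SAP 9.1, revise the wholly missing row and the year-only row (for AEs dated in the year of first dose), with one rule for both arms:

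- Assign the phase from the visit or call at which the AE was first reported, or from the AE's eCRF entry date if that contact is not captured. Count Visit 5 as double-blind, because OLE dosing starts at the end of that visit (Protocol 6.2.3).
- If that phase is the OLE, the partial date is compatible with OLE onset, and no stop date precedes OLE entry, impute the first OLE dose date. Otherwise impute the first double-blind dose date.
- Leave year-only dates in other years as they are.

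Also let the OLE-only summary count from the first OLE dosing day inclusive. Without this, the re-dated AEs would fall into neither phase table.

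In the example, blank and 2019 starts first reported in the OLE, with stop date blank or 1 October 2019, move to 28 June 2019 and enter the OLE and whole-study GNX summaries. A 2019 start with stop date 1 April 2019 stays at 1 March 2019.

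The change should not be limited to placebo subjects. Undated AEs would then leave the double-blind placebo column while GNX subjects' undated AEs stayed in theirs, biasing the randomized comparison against GNX.

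Cost: two table rows, one boundary and their programming, best settled before database lock. OLE AE counts may rise slightly. The documents do not show whether the first-reporting contact is recorded; the eCRF entry date is a rougher substitute, because entry may lag the visit by some days.
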